6.3.1 Baseline Data

Baseline and demographic characteristics will be summarized by standard descriptive statistics (including mean and standard deviation for continuous variables such as age and standard percentages for categorical variables such as gender).

6.3.2 Analysis of Primary Outcome of Interest

Daily cigarette and craving analyses

Hypothesis 1: Reported craving will be higher for those in the Tobacco retailer condition, relative to the Control and Nontobacco retailer conditions, during the intervention phase, but not the baseline phase. To test hypothesis 1, we will use a linear mixed effects model (in R). To examine associations between study phase and craving, we will create a binary Study Phase variable indicating whether an observation for a participant occurred during the baseline (0) versus intervention (1) phase. To examine associations between condition assignment and craving, we will create two dummy coded variables indicating the condition assignment for each participant. A Control condition variable indicates whether the condition assignment is the Control condition (1) or the other two conditions (i.e., Tobacco and nontobacco retailer) (0). A Nontobacco retailer condition variable indicates whether the condition is the Nontobacco retailer condition (1) or the other two conditions (i.e., Control and Tobacco retailer conditions) (0). Thus, the Tobacco retailer condition is indicated when both the Control condition and Nontobacco retailer condition variables are equal to 0. We will test the interactions between study phase and condition assignment.

At level 1, the formal model is constructed as:

$$\text{Craving}_{it} = \beta_{0i} + \beta_{1i}\text{StudyPhase}_{it} + e_{it}$$

where β_{0i} is the intercept, indicating the average level of craving for the prototypical participant in the sample; β_{1i} indicates the difference in the level of craving between the baseline phase and intervention phase; and e_{it} are residuals that are allowed to autocorrelate.

Person-specific intercepts and associations (from the Level 1 model) are specified (at Level 2) as:

$$\begin{aligned}\beta_{0i} &= \gamma_{00} + \gamma_{01}\text{ControlCondition}_i + \gamma_{02}\text{NontobaccoRetailerCondition}_i + u_{0i} \\ \beta_{1i} &= \gamma_{10} + \gamma_{11}\text{ControlCondition}_i + \gamma_{21}\text{NontobaccoRetailerCondition}_i + u_{1i}\end{aligned}$$

where the γ s are sample-level parameters and the u s are residual between-person differences that may be correlated with each other but are uncorrelated with e_{it} . Parameters γ_{11} and γ_{21} test the key hypotheses that craving will be higher for those in the Tobacco retailer condition, relative to the Control condition, during the intervention phase but not the baseline phase (γ_{11}) and that craving will be higher for those in the Tobacco retailer condition, relative to the Nontobacco retailer condition, during the intervention phase but not the baseline phase (γ_{21}).

Hypothesis 2: Reported cigarettes smoked will be higher for those in the Tobacco retailer condition, relative to the Control and Nontobacco retailer conditions, during the intervention phase, but not the baseline phase. To test hypothesis 2, we will use a linear mixed effects model (in R). To examine associations between study phase and cigarettes smoked, we will create a binary Study Phase variable indicating whether an observation for a participant occurred during the baseline (0) versus intervention (1) phase. To examine associations between condition assignment and cigarettes smoked, we will create two dummy coded variables indicating the condition assignment for each participant. A Control condition variable indicates whether the

condition assignment is the Control condition (1) or the other two conditions (i.e., Nontobacco retailer and Tobacco retailer conditions) (0). A Nontobacco retailer condition variable indicates whether the condition is the Nontobacco retailer condition (1) or the other two conditions (i.e., Control and Tobacco retailer conditions) (0). Thus, the Tobacco retailer condition is indicated when both the Control condition and Nontobacco retailer condition variables are equal to 0. We will test the interactions between the study phase and condition assignment.

At level 1, the formal model is constructed as:

$$Smoking_{it} = \beta_{0i} + \beta_{1i} StudyPhase_{it} + e_{it}$$

where β_{0i} is the intercept, indicating the average number of cigarettes smoked per day for the prototypical participant in the sample; β_{1i} indicates the difference in the level of craving between the baseline phase and intervention phase; and e_{it} are residuals that are allowed to autocorrelate.

Person-specific intercepts and associations (from the Level 1 model) are specified (at Level 2) as:

$$\begin{aligned}\beta_{0i} &= \gamma_{00} + \gamma_{01} ControlCondition_i + \gamma_{02} NontobaccoRetailerCondition_i + u_{0i} \\ \beta_{1i} &= \gamma_{10} + \gamma_{11} ControlCondition_i + \gamma_{21} NontobaccoRetailerCondition_i + u_{1i}\end{aligned}$$

where the γ s are sample-level parameters, and the u s are residual between-person differences that may be correlated with each other but are uncorrelated with e_{it} . Parameters γ_{11} and γ_{21} test the key hypotheses that the number of cigarettes smoked will be higher for those in the Tobacco retailer condition, relative to the Control condition, during the intervention phase but not the baseline phase (γ_{11}) and that the number of cigarettes smoked will be higher for those in the Tobacco retailer condition, relative to the Nontobacco retailer condition, during the intervention phase but not the baseline phase (γ_{21}).

for fMRI-related analyses:

Hypothesis 1: To test hypothesis 1 - that neural activity in smoking cue reactivity regions will be greater in response to standardized images of cigarette cues (standard smoking cues) than in response to standardized, approximately compositionally matched sets of images of non-cigarette cues (standard nonsmoking cues) - we will average neural activation across voxels in the aggregate craving ROI to assess differences in neural cue reactivity between standardized smoking cue blocks and standardized non-smoking cue blocks. Specifically, we will extract contrast estimates of each condition compared to rest, from the aggregate craving ROI. We will then use a linear mixed effects model (in R), to account for some participants having two sets of fMRI scans. To examine associations between neural activity in the cue reactivity ROI and the two task conditions (standard smoking and nonsmoking cues), we will create a binary TaskCondition variable indicating whether an observation occurred during the standard smoking cue blocks (1) vs standard non-smoking cue blocks (0). If we do not find a significant difference between these conditions in the ROIs defined in the pilot dataset using this approach, we will examine whole-brain effects using MarsBaR and will define cue reactivity ROIs for hypotheses 5 and 6 based on prior meta-analyses (e.g., Engelmann et al., 2012; Lin et al., 2020).

Lme (ROI ~ TaskCondition, random = ~ 1 | Participant / Session))

Where TaskCondition represents standard smoking cues vs standard nonsmoking cues.

Hypothesis 2: To test hypothesis 2 - that neural activity in smoking cue reactivity regions will be greater in response to viewing photos of the cash register area at a convenience store with tobacco marketing and products (tobacco retail images), than to photos of the cash register area at a pharmacy store without tobacco marketing and products (nontobacco retail images) -- we will use a parallel model to the model specified for Hypothesis 1, where for Hypothesis 2, the TaskCondition variable represents tobacco retail images vs nontobacco retail images.

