6.1 Sample Size and Power Determination

Our initial target was to obtain 60 complete datasets (meaning that participants finished Online Session 3, two fMRI sessions [before and after the intervention period], and also completed all 20 store visits) per intervention condition (total $N = 180$). Due to pandemic-related resource constraints and time delays, we were unable to reach this goal. We collected the maximum number of participants possible with the resources available from our grant. Prior to looking at the data, we elected to randomize more individuals into the experimental conditions than to the control condition, since less than 50% of participants typically completed all 20 store visits and provided fully complete datasets. Before we conducted any hypothesis testing, we reassessed power in consultation with our study team's biostatistician to determine which original hypotheses would be adequately powered with the available data and planned analysis.

methods. Using PANGEA, we estimated that with at least 40 complete datasets (participants who completed all 20 store visits) in each intervention condition, we could detect interaction effects (time * group) sized $d = 0.1$ with 95% power. We ultimately randomized 105 to the Non-tobacco retailer condition, 107 participants to the Tobacco retailer condition, and 70 participants to the Control condition resulting in 175 complete datasets. We scanned as many participants as we were able to obtain within constraints of the larger study. Power analysis suggests that with $N=32$ and at least 10 observations per condition in the fMRI dataset, per participant, we have $>80\%$ power to detect effects of $d = .2$ (i.e., a small effect size) within person.

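### The fMRI model for Hypotheses 1 and 2 does not account for repeat values in the contrast it tests, so its standard error is too small wherever a participant contributes more than one value per condition

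*Combined protocol and SAP*

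**What the plan says.** Section 6.3.2 gives one formula for the fMRI analyses: "Lme (ROI ~ TaskCondition, random = ~ 1 | Participant / Session". Its random part, "random = ~ 1 | Participant / Session", has an intercept for each participant and for each session within participant, and no participant-level TaskCondition effect. The stated reason for a mixed model is "to account for some participants having two sets of fMRI scans". For Hypothesis 2 (tobacco versus nontobacco retail images) the plan says "we will use a parallel model to the model specified for Hypothesis 1".

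The row of data that enters the model is not settled. Section 6.3.2 says "we will extract contrast estimates of each condition compared to rest, from the aggregate craving ROI", which reads as one value per condition per session. The same paragraph defines the TaskCondition indicator by the type of cue block in which an observation fell. Section 6.1 bases the fMRI power statement (N=32, d=0.2, more than 80%) on "at least 10 observations per condition in the fMRI dataset, per participant".

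The number of participants with two sets of scans is not stated. Sections 3.3, 4.1, 5.3.4 and 11.3 describe a single optional scan. Two scans per person appear in Section 6.1 only as part of the initial target.

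Brain activity is the primary endpoint for the scan session (3.4.1), and the tests are two-sided at 0.05 (6.2). The craving and smoking models in Section 6.3.2 do include a person-specific phase effect, u1i.

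**The concern.** TaskCondition varies within a session. Anything constant within a person or a session, which is all that a random intercept describes, drops out of the smoking-minus-nonsmoking difference. The formula has no term for a person whose cue effect is consistently large or small. If such a person contributes two differences, the model counts them as two independent pieces of evidence. The nesting chosen to handle repeat scans therefore does not handle them for the effect being tested. If several observations per condition are entered, the same happens within a single session.

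The result would be confidence intervals for cue reactivity that are too narrow and a false-positive rate above 5% for both hypotheses. The Hypothesis 1 result also decides whether the pilot-defined regions are kept for later hypotheses or replaced by regions taken from meta-analyses, so an error there carries forward.

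**Working it through.** **Inputs from the plan.** N=32; at least 10 observations per condition per participant; d=0.2; power above 80% (6.1). Two-sided alpha 0.05 (6.2). Intercept-only model (6.3.2).

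**Inputs assumed, because the plan does not give them.** The fraction f of participants scanned twice; the between-session correlation r of a person's cue effect; the person-by-cue variance τ²; the residual variance σ²; the intraclass correlation (ICC).

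**1. The plan's power figure.** It cannot be reproduced exactly, because the standardiser of d and the variance components are not stated. Take d in units of the total SD and 32 × 10 = 320 observations per condition, all independent for the cue effect. Then SE = √(2(1−ICC)/320).
- ICC 0: SE = 0.0791, and power = Φ(0.2/0.0791 − 1.96) = 72%.
- Power reaches 80% at an ICC of about 0.185, and is 86% at 0.3.
- If d=0.2 is instead the standardised paired difference, power is 95% on 320 pairs but 20% on 32 persons.

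Under these readings, more than 80% is reached only if repeated observations count as nearly independent information on the cue effect.

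**2. One session, one estimate per condition.** Each person supplies one difference, and differences between people in the cue effect fall into the residual. On a simulated data set of 32 people, the random-intercept SE was 0.16326 and the paired-t SE was 0.16326. Simulated type I error was 5.0%.

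**3. One estimate per condition per session, some people scanned twice.** The model treats N(1+f) session differences as independent. The true variance exceeds the model's by the ratio 1 + 2fr/(1+f). The approximate type I error divides the t critical value, on N(1+f)−1 df, by the square root of that ratio.

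| Scanned twice | r | Variance ratio | SE ratio | Type I error |
|---|---|---|---|---|
| 8 of 32 (f=0.25) | 0.3 | 1 + 0.15/1.25 = 1.12 | 1.06 | 6.3% |
| 8 of 32 | 0.5 | 1 + 0.25/1.25 = 1.20 | 1.10 | 7.2% |
| 16 of 32 (f=0.5) | 0.3 | 1 + 0.30/1.5 = 1.20 | 1.10 | 7.3% |
| 16 of 32 | 0.5 | 1 + 0.50/1.5 = 1.33 | 1.15 | 8.8% |

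Simulation agrees to within about 0.3 percentage points. The rounded ranges are 6.4% to 7.4% and 7.5% to 8.8%. At the low end, with 5 of 32 scanned twice and r=0.2, type I error is 5.6%.

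**4. Ten observations per condition per person, one session.** With σ²=1:
- true variance = (τ² + 2/10)/32;
- model variance = s² × 2/320, where s² = [32×18 + 5×31×(τ² + 0.2)]/607 is the pooled residual that absorbs part of τ².

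| τ²/σ² | True SE | Model SE | SE ratio | Type I error |
|---|---|---|---|---|
| 0.05 | 0.0884 | 0.0796 | 1.11 | about 8% |
| 0.10 | 0.0968 | 0.0801 | 1.21 | about 11% |
| 0.20 | 0.1118 | 0.0811 | 1.38 | about 16% |

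In simulation, the SE from averaging to one difference per person was wider by about 10%, 20% and 37%.

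**5. Test on one averaged difference per person.** Simulated type I error stays at about 5% in every scenario of steps 3 and 4.

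**6. Power of that test under step 4.** Use SE = √((τ² + 2σ²/10)/32) with σ² = 1−ICC, and a noncentral t on 31 df. For example, with ICC 0.3 and τ²/σ² = 0.05, SE = √((0.035+0.14)/32) = 0.0740, the noncentrality is 0.2/0.0740 = 2.70, and power is 75%.

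| τ²/σ² | Power, ICC 0.3 | Power, ICC 0.5 |
|---|---|---|
| 0 | 83% | 93% |
| 0.05 | 75% | 87% |
| 0.10 | 67% | 81% |
| 0.20 | 54% | 69% |

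**The case against.** A reader might infer from the missing slope that the standard error is too small for every participant. The documents do not support that. The most natural reading of the extraction step is one contrast estimate per condition per session, and for anyone scanned once the model is then a paired t-test with a correct standard error.

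A reader might also take the worst case, with all 32 scanned twice, where type I error is about 11% at r=0.5. Section 6.3.2 says only that some were, and the procedures describe one optional scan. The fraction may be small and the inflation with it.

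The observation-level figures need several rows per condition in the model. The 10 observations in Section 6.1 could instead be the trials or blocks behind each contrast estimate, and the block wording in Section 6.3.2 fits that too. The values of r and τ² are assumptions.

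All of this limits the size of the problem and stands. It does not remove the mechanism: the plan itself says that repeat scans exist and that the model is there to deal with them, and for the tested contrast it does not. A participant slope may also be a weak remedy, because with one estimate per condition per session only the twice-scanned people separate it from residual error.

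**Conclusion.** The concern holds in conditional form. Wherever a participant contributes more than one value per condition, the specified model gives a standard error for Hypotheses 1 and 2 that is too small, provided a person's cue effects are positively correlated across those values. If only repeat sessions are involved, the inflation is modest: about 6.4% to 7.4% with a quarter scanned twice and 7.5% to 8.8% with half (N=32, r assumed 0.3 to 0.5). If about 10 observations per condition per person are entered, it is about 8% to 16% for an assumed person-by-cue variance of 5% to 20% of residual variance.

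The direction is clear. The size is not, because the unit of observation, the repeat-scan count, r and τ² are all missing. The documents do not show that the standard error is wrong for participants with a single scan and one estimate per condition.

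**What to change.** 1. Make the primary test of each hypothesis a one-sample t-test on one difference per participant (smoking minus nonsmoking cues for Hypothesis 1, tobacco minus nontobacco retail images for Hypothesis 2), averaged over sessions and observations, on N−1 df (31 if N=32).
2. Alternatively, add a participant-level random slope for TaskCondition if there are enough repeat values to estimate it. This would match the person-specific effect already in the craving and smoking models.
3. State what one row of the analysis data is, and how many participants have two sets of scans.
4. Restate the fMRI power on that basis, with the definition of d and the assumed variance components.

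**Cost.** A line of code and a few sentences in Sections 6.1 and 6.3.2. If few people have repeat values, the results hardly change. Under the observation-level reading the standard error widens by roughly 10% to 37%, and the stated power may fall below 80%.

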6.3.3 Interim Analysis

At two time points during data collection, we will assess whether the study is producing unexpectedly positive or negative effects on participant outcomes. After collection of 60 participants (approximately 20 in each group) and 120 participants (approximately 40 in each group), we will test whether individuals in the Tobacco retailer condition have significantly changed the number of cigarettes that they smoke per day (as described in 5.7). If this group of participants changes their cigarette consumption by a clinically significant level, we will stop assigning participants to that group and assign all further participants equally to the other groups.

7 Safety and Adverse Events

7.1 Definitions

7.1.1 Adverse Event

An adverse event (AE) is any symptom, sign, illness or experience that develops or worsens in severity during the course of the study. Intercurrent illnesses or injuries should be regarded as adverse events.

Incidental findings in the fMRI component of this study are considered to be adverse events if the finding:

- results in study withdrawal
- is associated with a serious adverse event
- is associated with clinical signs or symptoms
- leads to additional treatment or to further diagnostic tests
- is considered by the investigator to be of clinical significance

7.1.2 Serious Adverse Event

Serious Adverse Event

Adverse events are classified as serious or non-serious. A serious adverse event is any AE that is:

- fatal
- life-threatening
- requires or prolongs hospital stay
- results in persistent or significant disability or incapacity
- required intervention to prevent permanent impairment or damage
- a congenital anomaly or birth defect
- an important medical event

7.2 *Recording of Adverse Events*

Smoking behavior will be self-reported at each study session and multiple times daily during the baseline and intervention periods. This data will be used at set points as described in section 5.7. Experimenters will record medical or other life events that may be considered adverse events as reported by participants (e.g., hospitalization or injury in between study sessions). Information on all adverse events will be recorded in the source document immediately upon discovery, and also in the appropriate adverse event module of the case report form (CRF). All clearly related signs, symptoms, and abnormal incidental findings results will be recorded in the source document.

All adverse events occurring during the study period will be recorded. The clinical course of each event will be followed until resolution, stabilization, or until it has been determined that the study intervention or participation is not the cause. Serious and related adverse events that are still ongoing at the end of the study period will be followed up to determine the final outcome. Any serious adverse event that occurs during an in-person session and is considered to be possibly related to the study intervention or study participation will be recorded and reported.

7.3 *Relationship of AE to Study*

- **Definitely Related** – There is clear evidence to suggest a causal relationship, and other possible contributing factors can be ruled out. The clinical event, including an abnormal laboratory test result, occurs in a plausible time relationship to study procedures administration and cannot be explained by concurrent disease or other drugs or chemicals. The response to withdrawal of the study procedures should be clinically plausible. The event must be pharmacologically or phenomenologically definitive.
- **Probably Related** – There is evidence to suggest a causal relationship, and the influence of other factors is unlikely. The clinical event, including an abnormal laboratory test result, occurs within a reasonable time after administration of the study procedures, is unlikely to be attributed to concurrent disease or other drugs or chemicals, and follows a clinically reasonable response on withdrawal.
- **Potentially Related** – There is some evidence to suggest a causal relationship (e.g., the event occurred within a reasonable time after administration of study procedures). However, other factors may have contributed to the event (e.g., the participant's clinical condition, other concomitant events). Although an AE may rate only as "possibly related" soon after discovery, it can be flagged as requiring more information and later be upgraded to "probably related" or "definitely related", as appropriate.
- **Unlikely to be related** – A clinical event, including an abnormal laboratory test result, whose temporal relationship to study procedures administration makes a causal relationship improbable (e.g., the event did not occur within a reasonable time after administration of the study procedures) and in which other drugs or chemicals or underlying disease provides plausible explanations (e.g., the participant's clinical condition, other concomitant treatments).
- **Not Related** – The AE is completely independent of study procedures administration, and/or evidence exists that the event is definitely related to another etiology.

The PI will make this determination.

7.4 *Reporting of Adverse Events and Unanticipated Problems*

The Investigator will promptly notify the Penn IRB of all on-site unanticipated, Serious Adverse Events that are related to the research activity. Other unanticipated problems related to the research involving risk to subjects or others will also be reported promptly. Written reports will be filed using the HS-ERA and in accordance with the Penn IRB timeline of 10 working days. All instances of related SAEs will be reported to the appropriate IRB and the NCI Program Officer within 24-hours of discovery, whereas probably or definitely related SAEs will be reported to the appropriate IRBs within 10 days of occurrence using the on-line system.

